## 3.2. General Description of Investigative Agent(s)/Device

### Radiopaque Beads

A current limitation in improving the accuracy of embolic administration during TACE and in understanding how well the treatment is reaching its target is the inability to visualise the beads used to deliver the drug locally within the liver. BTG has recently developed a radiopaque (RO) bead that can be visualised with CT or fluoroscopic imaging and have the advantage of providing intra and post-procedural visible confirmation of bead location during the embolisation procedure, enabling real-time adjustments to optimise patient treatment (Johnson et al., 2016). The radiopaque bead builds on existing DC Bead™ technology used to embolise the blood vessels and deliver drugs at high concentrations to tumours. The lasting radio-opacity of RO beads means that they are visible on X-ray based follow-up scans, allowing precise evaluation of the completeness of tumour treatment.

RO beads are commercially available in the US (as LC Bead LUMI™) for the treatment of hypervascularised tumours and arteriovenous malformations. In Canada, DC Bead LUMI™ is approved for the treatment of HCC in combination with doxorubicin and for the treatment of mCRC in combination with irinotecan. BTG-002814 is an imageable product based on the BTG RO bead platform. It is a pre-loaded, RO bead with a size range of 60–160 µm and is provided in a 20 mL glass vial. In addition, the 60-160 µm size range in the BTG-002814 formulation was chosen to ensure tumour penetration by the embolic agent and to maximise drug exposure to the tumour tissue.

### Vandetanib

Vandetanib is a potent inhibitor of the tyrosine kinase activity of VEGFR-2, an endothelial cell receptor for vascular endothelial growth factor (VEGF). It also possesses activity against EGFR and REarranged during Transfection (RET) tyrosine kinases. VEGF is a potent stimulator of new blood vessel growth (angiogenesis) and plays an essential role in the formation and maintenance of the vasculature by activating protease expression, endothelial cell proliferation and migration, and capillary vessel formation. Pathological angiogenesis is necessary for the progression of solid, malignant tumours and inhibition of VEGF-dependent signaling has been identified as a key anti-angiogenic strategy (Ferrara, 2004).

EGFR-dependent signaling is an important pathway contributing to the growth and metastasis of tumour cells, and aberrant EGFR tyrosine kinase activity has been reported in a number of human solid tumours. EGFR tyrosine kinase activity plays a key role in numerous processes that affect tumour growth and progression, including proliferation, dedifferentiation, inhibition of apoptosis, metastasis and angiogenesis (Vlahovic & Crawford, 2003).

By targeting both angiogenesis and EGFR- and RET-dependent tumour cell growth, it is hypothesised that the growth of tumours will be controlled, with relative sparing of normal tissues. The oral version of vandetanib, branded as Caprelsa®, is approved for the treatment of patients with advanced medullary thyroid cancer.

Phase 1 dose-escalation studies performed in Western and Japanese patients, with solid tumours refractory to standard therapy, showed that vandetanib was generally well tolerated at daily doses up to 300 mg (Holden et al., 2005; Tamura et al., 2006). Vandetanib can significantly prolong progression-free survival (PFS) of patients with advanced medullary thyroid cancer (Wells et al., 2010) and is not inferior to erlotinib as a second-line therapy for patients with advanced non-smallcell lung cancer (NSCLC) (Natale et al., 2011). Vandetanib plus docetaxel can significantly

prolong PFS, compared with docetaxel alone, in patients with advanced NSCLC after progression following first-line chemotherapy (Herbst et al., 2010).

Systemic therapy with oral vandetanib has been investigated in a clinical setting in a broad range of human malignancies, including HCC and mCRC. Some of these clinical studies are reviewed below.

### **Systemic vandetanib treatment of HCC**

Sixty-seven HCC patients were randomised to oral vandetanib 300 mg (n=19), oral vandetanib 100 mg (n=25) or placebo (n=23). Twenty nine patients subsequently entered open-label treatment. Vandetanib induced a significant increase in circulating VEGF and decrease in circulating VEGFR levels. In both vandetanib arms, tumour stabilisation rate was not significantly different from placebo. Although trends towards improved PFS and Overall Survival (OS) after vandetanib treatment were found, they were not statistically significant. The most common adverse events were diarrhoea and rash in both treatment groups (Hsu et al., 2012).

### **Systemic vandetanib treatment of colorectal cancer**

A number of phase 1 dose escalation studies were conducted to determine the maximum tolerated dose (MTD) of vandetanib in combination with different therapeutic agents and regimens, predominantly in mCRC patients. In a study of 21 patients with vandetanib 100 mg (n=11) and vandetanib 300 mg (n=10) combined with standard 14-day treatment cycles of FOLFIRI, the most commonly reported AEs were diarrhoea, fatigue and nausea. In one study of vandetanib combined with cetuximab and irinotecan, 27 patients were enrolled at 4 dose levels. Two dose-limiting toxicities (DLTs) (grade 3 QTc prolongation and diarrhoea) were detected at 300 mg vandetanib with cetuximab and irinotecan resulting in 200 mg being the MTD (Meyerhardt et al., 2012). In another study, 13 patients received vandetanib at doses of 100 mg and 300 mg daily in combination with capecitabine and oxaliplatin, which was well tolerated. However, the addition of bevacizumab resulted in severe diarrhoea in three out of four patients. Bevacizumab was not well tolerated with vandetanib and XELOX in combination (Cabebe, Fisher & Sikic, 2012). In 17 patients with advanced mCRC, vandetanib 100 mg (n=9) or 300 mg (n=8) was combined with mFOLFOX6 chemotherapy. The most commonly reported AEs were diarrhoea, lethargy and nausea. The CTCAE Grade 3/4 events that were considered to be related to vandetanib was Grade 3 diarrhoea in 3 patients (1 patient in the 100 mg cohort and 2 patients in the 300 mg cohort) and Grade 3 thrombocytopenia in 1 patients (300 mg cohort) (Michael, Gibbs, Smith, Godwood, Oliver & Tebbutt, 2009). In another study to assess the effect of vandetanib on vascular permeability in patients with advanced CRC and liver metastases, 22 patients received the study drug; 10 received 100 mg and 12 received 300 mg. The most commonly reported AEs were diarrhoea, dry mouth, fatigue and nausea (Mross et al., 2009).

Two phase II, double-blind, placebo-controlled, randomised studies were conducted to assess the efficacy and safety of 2 doses of vandetanib (100 mg and 300 mg) in combination with FOLFOX or FOLFIRI in patients who had failed with FOLFIRI (109 patients) or FOLFOX (121 patients) regimens respectively. The addition of vandetanib to FOLFOX regimen did not show any additional benefit in terms of number of patients with disease progression and the time to progression. A lower risk of disease progression was reported with 100 mg vandetanib combined with FOLFIRI regimen compared to the FOLFIRI regimen with placebo (57% vs 69%). The percentages of patients who had a disease progression event in the vandetanib 300 mg group and placebo group were similar (67% vs 69%). The estimated median times to progression were 114 days for the vandetanib 100 mg group, 151 days for the vandetanib 300 mg group, and 103 days for the placebo group. The safety profile of vandetanib (100 mg and 300 mg) in combination

with both regimens, FOLFOX and FOLFIRI, was acceptable. The most commonly reported AEs were diarrhoea and nausea; thrombocytopenia was reported with FOLFOX-vandetanib and neutropenia with FOLFIRI-vandetanib.

### 3.3. Pre-Clinical Background of Investigative Agent(s)/Device

#### *In vitro* pharmacology

Vandetanib is a potent inhibitor of VEGFR-2 tyrosine kinase activity with an  $IC_{50}$  value of 40 nM. In isolated enzyme assays, vandetanib was also found to be a sub-micromolar inhibitor of fmslike tyrosine kinase (Flt)-4 (VEGFR-3, the VEGF-C and -D receptor:  $IC_{50}$  =110 nM) and EGFR tyrosine kinases ( $IC_{50}$  = 500 nM). Additional vandetanib activity has been demonstrated against oncogenic RET kinase ( $IC_{50}$  = 100 nM) which is activated in certain thyroid carcinomas.

Further details are provided in the BTG-002814 Investigator Brochure.

#### *In vivo* pharmacology

Vandetanib has demonstrated broad spectrum anti-tumour angiogenesis activity in several histologically diverse tumour xenograft models (lungs, prostate, breast, ovarian, colon). Chronic once daily oral administration (12.5-100 mg/kg/day) produced significant dose dependent inhibition of tumour growth. Vandetanib has also been shown to inhibit growth of tumours implanted orthotopically e.g. orthotopic models of gastric and pancreatic cancer. In mouse models of human prostate and colon cancer, DCE-MRI analysis showed a dose dependent reduction in contrast agent uptake by tumour 24 hours after initiating therapy with vandetanib, consistent with vandetanib inhibition of VEGF induced permeability in tumour vasculature (Ryan & Wedge, 2005). Vandetanib inhibited tumour growth of hepatoma cells in subcutaneous mouse tumour model. In addition, vandetanib suppressed phosphorylation of VEGFR-2 and EGFR in tumour tissues, significantly reduced tumour vessel density, enhanced tumour cell apoptosis, improved survival, reduced number of intra-hepatic metastases and upregulated VEGF, TGF- $\alpha$  and EGF in tumour tissues (Inoue et al., 2012).

Further details are provided in the BTG-002814 Investigator Brochure.

#### Pre-clinical background of BTG-002814

The safety of the vandetanib-eluting bead has been evaluated in a GLP swine liver embolisation model. In this model, vandetanib-loaded RO beads (100 mg vandetanib per 1 mL bead) were delivered to healthy liver by hepatic intra-arterial administration. Up to 1 mL of vandetanib-loaded bead was administered, which equates to delivery of 100 mg vandetanib to the targeted liver lobe. The animals were maintained for either 30 or 90 days. There were no treatment-related effects evident in parameters evaluated, namely, clinical observations, body weight, ophthalmoscopy, ECG, and organ weights. Transient changes in coagulation and clinical chemistry parameters were observed, likely to be related to the hepatic embolisation procedure.

There were expected microscopic findings associated with hepatic embolisation following intrahepatic administration of vandetanib-loaded bead. The study indicated that intrahepatic administration of up to 1 mL vandetanib-loaded RO bead containing 100 mg of vandetanib was well tolerated, did not produce any obvious systemic toxicity and resulted in nothing more than expected microscopic findings associated with hepatic embolisation and subsequent healing.

In an efficacy study conducted in a rabbit model, VX-2 carcinoma tumours were implanted in the liver, followed by hepatic intra-arterial administration of DC Bead loaded with vandetanib up to 135 mg/mL (DCV). DCV showed equivalent anti-tumoural activity to doxorubicin-loaded bead and superior anti-tumoural activity compared to bland (unloaded) bead. Single hepatic administration of DCV showed equivalent anti-tumoural efficacy to repeat dose of oral vandetanib, at the doses administered (~5.4 mg per animal with DCV vs 1470 mg oral vandetanib, respectively). Compared to oral dosing, it is notable that DCV showed a lower plasma concentration and a higher tumour concentration of vandetanib relative to the total dose administered.

## 4. STUDY RATIONALE, OBJECTIVES and DESIGN

### 4.1. Study Rationale

TACE is the current standard of care for patients with intermediate-stage HCC and is also a treatment option for patients with mCRC. Despite advances and technical refinements of TACE, including the introduction of drug-eluting beads (DEB)-TACE, the long term survival of patients managed with TACE is generally poor, mainly as a result of the high rates of tumour recurrence. Improving the technique used for DEB-TACE, by being able to visualise the beads on CT scans, and by developing the ability to load new anti-cancer molecularly targeted drugs on to the beads, specifically vandetanib, are two important approaches to potentially improving the efficacy of TACE for patients with HCC or mCRC.

This clinical trial will study the feasibility of administering radiopaque beads loaded with vandetanib, a tyrosine kinase inhibitor that targets both VEGFR and EGFR signaling pathways, as two novel approaches combined in to one new therapy, BTG-002814, to enhance anti-tumour efficacy compared to current liver-directed therapies. It will be the first time that BTG-002814 has been administered to humans. Since cTACE can be safely used in the pre-operative setting to treat cancers prior to liver surgery, this study will be performed in resectable patients with HCC and mCRC, therefore providing a ‘window of opportunity’ to measure the levels of vandetanib in the resected liver sample, as well as assessing the safety and tolerability of BTG-002814 in patients with cancer. Tumour recurrence rates for HCC and mCRC after liver surgery are currently up to 50% of patients, so the development of any pre-operative therapy with the potential to improve the chances of long-term disease control following surgery is an important research goal.

### 4.2. Study Objectives

#### 4.2.1. Primary Objectives

- To assess the safety and tolerability of treatment with BTG-002814
- Measure the plasma and resected liver tissue concentrations of vandetanib and the Ndesmethyl metabolite following treatment with BTG-002814

#### 4.2.2. Secondary Objectives

[figure not shown]
- Evaluate the anatomical distribution of BTG-002814 on non-contrast enhanced imaging using 4D CT
- Evaluate histopathological features in the surgical specimen following treatment with BTG002814
- Assess changes in blood flow on dynamic contrast-enhanced magnetic resonance imaging (DCE-MRI) following treatment with BTG-002814

#### 4.2.3. Exploratory Objective

- Study blood biomarkers with the potential to identify patients likely to respond to treatment with BTG-002814
- Study tissue biomarkers to explore key immune, inflammatory and drug related mechanisms
- Correlate the distribution of BTG-002814 on imaging with pathology by 3D modelling

## 4.3. Study Design

### 4.3.1. Study Design Flow Chart

### 4.3.2. Summary of Study Design

A pilot, open-label, single arm, multicentre, phase 0, window of opportunity study with DEB-TACE treatment with BTG-002814 given between 1 and 3 weeks prior to surgery in up to 12 patients with resectable HCC or mCRC.

Three patients who have either HCC or liver metastases from CRC and who are candidates to receive surgery will initially be enrolled.

An interim analysis conducted by a Safety Committee (SC) is planned when the first three patients complete the last follow-up visit scheduled at 4 weeks after surgery.

If the SC deems that there is no significant toxicity related to BTG-002814, a further 9 patients will be enrolled in order to have a target sample size of 6 patients with HCC and 6 patients with liver metastases from CRC.

A final analysis will be performed when 12 patients complete the last follow-up visit, or once 14 patients have been enrolled and are no longer on study. All patients will receive one treatment of BTG-002814.

## 4.4. Randomisation

This is a single arm study; so randomisation is not applicable.

## 4.5. Study Endpoints

### 4.5.1. Co-Primary Endpoints

- Adverse events (AEs) related to treatment with BTG-002814 using the standardised grading criteria (National Cancer Institute Common Terminology Criteria for Adverse Events Version 4.0 (NCI-CTCAE v4.0))
- Concentration of vandetanib and N-desmethyl vandetanib in plasma and in resected liver tissue following treatment with BTG-002814.

### 4.5.2. Secondary Endpoints

- Distribution of BTG-002814 on non-contrast enhanced imaging of tumour vasculature and regions of interest using 4D CT
- Evaluation of histopathological features in the surgical specimen (malignant and nonmalignant liver tissue): tumour necrosis, viable tumour, vascular changes
- Assessment of changes in blood flow on DCE-MRI following treatment with BTG-002814. The following parameters will be derived from DCE-MRI images: Ktrans, Kep and Ve

### 4.5.3. Exploratory Endpoints

- Study blood biomarkers with the potential to identify patients likely to respond to treatment with BTG-002814
- Study tissue biomarkers to explore key immune, inflammatory and drug related mechanisms
- Correlate the distribution of BTG-002814 on imaging and pathology by 3D modelling

## 5. PATIENT SELECTION

### 5.1. Patient Population

The study population will consist of patients with HCC or liver metastases from CRC who are deemed suitable for liver surgery.

### 5.2. Subject Selection

#### 5.2.1. Inclusion Criteria

1. Male or female adults ( $\geq 18$  years old)
2. Patient with resectable HCC (Child Pugh A, INR  $\leq 1.5$ ) or resectable liver metastases from CRC and a candidate for liver surgery
3. Patients with low risk for surgical morbidity and mortality from liver surgery according to the investigator's judgement
4. WHO performance status 0, 1 or 2
5. Adequate haematological function with Hb  $>90$  g/L, absolute neutrophil count  $>1.5 \times 10^9/L$ , Plt  $>75 \times 10^9/L$
6. Adequate liver function with serum bilirubin  $<1.5 \times ULN$ , ALT (or AST if ALT not available)  $\leq 5 \times ULN$ , ALP  $<5 \times ULN$
7. Adequate renal function with serum creatinine  $\leq 1.5 \times ULN$  and calculated creatinine clearance (GFR)  $\geq 50$  mL/min estimated using a validated creatinine clearance calculation (e.g. Cockcroft-Gault or Wright formula).
8. Patient is willing to provide blood samples, and tissue samples at surgical resection, for research purposes
9. Patient is willing and able to provide written informed consent

#### 5.2.2. Exclusion Criteria

1. Any systemic chemotherapy within 3 months of the screening visit or any plan to administer systemic chemotherapy prior to surgery
2. Previous treatment with transarterial embolisation (with or without chemotherapy) of the liver, prior radiotherapy or ablation therapy to the liver or prior yttrium-90 microsphere therapy
3. Any contraindication to vandetanib according to its local label including:
  - Hypersensitivity to the active substance
  - Congenital long QTc syndrome
  - Patients known to have a QTc interval over 480 milliseconds
  - Concomitant use of medicinal products known to also prolong the QTc interval and/or induce Torsades de pointes (see Appendix 1)
4. Any contraindication to hepatic artery catheterisation or hepatic embolisation procedures (e.g. portal venous thrombosis, severely reduced portal venous flow or hepatofugal blood flow, untreated varices at high risk of bleeding)
5. Women of child-bearing potential not using effective contraception or women who are breast feeding
6. Confirmed allergy to iodine-based intravenous contrast media
7. Patients who cannot have CT, MRI or DCE-MRI Imaging (according to site policy)
8. Active uncontrolled cardiovascular disease

9. Any co-morbid disease or condition or event that, in the investigator's judgement, would place the patient at undue risk and would preclude the safe use of DEB-TACE with BTG002814
10. Levels of potassium, calcium, magnesium or thyroid stimulating hormone (TSH) outside of the normal ranges, and that in the investigator's judgment are clinically significant, or other laboratory findings that in the view of the investigator makes it undesirable for the patient to participate in the study
11. Patients who have received treatment in another clinical trial with an investigational medicinal product within 4 weeks prior to the screening visit

### 5.3. Reproductive Potential

All women of child-bearing potential (WOCBP) enrolled into this study will have a serum pregnancy test at Screening (Visit 0) to assess their suitability for entry into the study. Women who are pregnant or who are breast feeding are excluded from this study.

#### ***Definition of WOCBP***

A WOCBP is a sexually mature woman (i.e. any woman who has experienced menstrual bleeding) who has not:

- undergone a hysterectomy or bilateral oophorectomy/salpingectomy
- been postmenopausal for 12 consecutive months (i.e. who has had menses at any time in the preceding 12 consecutive months without an alternative medical cause)
- had premature ovarian failure confirmed by a specialist gynaecologist
- XY genotype, Turner syndrome, uterine agenesis

WOCBP, or any male patient enrolled in the study who has a WOCBP partner, must use effective contraception during the study and for four months after treatment.

Acceptable methods of contraception include established use of oral, injected or implanted hormonal birth control, intrauterine device, or barrier method in conjunction with spermicidal foam/cream/jelly/suppository, female/male sterilisation or abstinence where this is the patient's preferred and usual lifestyle.

### 5.4. Patient Completion

Patient enrolment is planned to continue until the target number of 12 patients have been included.

Patients will complete the study 28-32 days following the surgical resection.

### 5.5. Patient Withdrawal

Patients may withdraw from the study at any time for any reason without prejudice to their future medical care by the physician or at the institution. The Investigator or Sponsor may withdraw the patient at any time (e.g., in the interest of patient safety). The withdrawal of a patient from the study by the Investigator should be discussed where possible with UCL CTC and the Sponsor.

For patients who withdraw before the end of the study, all Visit 6 (End of Study) assessments should be completed, if possible, prior to withdrawal. All AEs must be documented in the patient medical notes and case report forms (CRF).

If a patient withdraws from the study for any reason, all efforts should be made to follow AEs as described in section 8, unless the patient withdraws consent.

A maximum of 2 patients who withdraw from the study early will be replaced.

## **5.6. Patients “Lost to Follow-up” Prior to Last Scheduled Visit**

At least 3 documented attempts must be made to contact any patients Lost to Follow-up at any time point prior to the last scheduled visit.

## 6. TREATMENT OF PATIENTS

### 6.1. Vandetanib-eluting radiopaque bead (BTG-002814)

#### 6.1.1. Dosage & Administration

All patients will receive one treatment of BTG-002814. One vial of BTG-002814 will be used for each patient.

To hydrate BTG-002814, 1 mL of Water For Injection followed by 9 mL of Omnipaque 350 contrast agent will be added to the vial. The full contents of the vial will be delivered slowly (approximately 1 min per mL) under fluoroscopic visualisation while observing the contrast flow rate, through an intra-arterially placed microcatheter and must be used within 4 hours of reconstitution. Full instructions for use will be provided in the Summary of Drug Arrangements (SoDA).

#### Embolisation procedure

Using a unilateral femoral approach, selective catheterisation of the hepatic artery will be performed. Diagnostic visceral arteriography will be performed to delineate the arterial supply to the tumour, determine the presence of variant arterial anatomy and to confirm patency of the portal vein. Once the patient's arterial anatomy is understood, a catheter is advanced into the right or left hepatic artery distal to the cystic artery (if visualised). The treatment plan is based on the fluoroscopic appearances during arteriography. For the purposes of this clinical trial, since all eligible patients have resectable disease, it is not a requirement of the protocol that all lesions visible on CT are treated with BTG-002814. This decision will be at the discretion of the treating investigator. For example, if a right hemihepatectomy is the operation planned, it is not necessary to treat all the lesions in the anterior and posterior sector; the lesions to be treated may be those deemed to be at highest risk of a positive surgical resection margin and therefore at highest risk of tumour recurrence following surgery. It is important to confirm the location of delivered beads on 4D CT at the end of the procedure relative to the treatment plan based on fluoroscopic appearances.

Once the catheter is in place within the artery feeding the tumour, the re-constituted BTG-002814 suspension will be slowly infused into the artery (approximately 1 mL per minute). Catheter selection will be by operator preference. There will not be any issues with a 4- or 5-Fr catheter, but the choice of a microcatheter, in case of tortuous, narrow or spastic vessels must be consistent with the size of embolic agent used (see IFU). The end point of the procedure is either full delivery of the reconstituted bead volume (i.e. 1 mL beads + vandetanib + contrast) or stasis in the tumoural vessel over 2-5 cardiac cycles. Undelivered volume of reconstituted embolic solution must be recorded.

For HCC patients, a super selective (segmental/subsegmental) approach should be taken with the catheter placed as selectively as possible whilst maintaining sufficient flow to the tumour. For mCRC patients, it is generally a lobar approach, by placing the catheter tip beyond the origin of the cystic artery (or any other arteries supplying extrahepatic organs) and maintaining forward flow.

The catheter will then be removed and haemostasis achieved by manual compression or with a percutaneous closure device. Each patient will be admitted for overnight care.

The amount of contrast agent delivered to the patient during the procedure and skin dose of xrays from fluoroscopy will be recorded as well as the time exposed to fluoroscopic imaging. The vessels embolised will be noted and the amount of embolic agent used will be recorded. All medications used during the procedure will be recorded, including pain management regime.

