4.2.2 Resected tissue

For each patient, provide a concentration-time plot for:

- vandetanib
- N-desmethyl metabolite

(concentration as the y-axis and time as the x-axis).

Each plot would be indicated as to whether the patient had HCC or mCRC.

This will be for:

- malignant tissue – three measurements for each patient:
 - Centre of tumour
 - Mid tumour
 - Edge of tumour
- non-malignant tissue
 - 1 cm from the edge of the tumour
- paired samples (difference, per patient, using malignant (based on the average of the 3 locations/samples) minus non-malignant values). Can be analysed using a t-test or non-parametric test
- Describe technical reasons for missing data points

5. Secondary objectives/outcomes (other blood, tissue and imaging markers)

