6.2. Tumour size/measurement

- The longest diameter of each lesion (mm) is measured at baseline and again on the day before surgical resection.
- The sum of the diameters can be taken for each patient, using the same lesions.
- Produce a waterfall plot showing the change in the sum from baseline to pre-surgery.
- Change in tumour size can also be compared using a paired t-test or Mann-Whitney test, depending on whether Normally distributed or not.
- Waterfall plot obtained for all patients, then separately for HCC and mCRC.

7. Concomitant Medications

Patient ID	Drug name/type	Time (days) from day of BTG treatment to start of non-trial drug
1	A	
1	B	
1	C	
2	D	
2	E	
2	F	

8. Follow up and deaths

	All patients	HCC	mCRC
	n (%)	n (%)	n (%)
No. patients who died			
Cause of death			
No. patients who dropped out/withdrew from the trial			
Reasons for withdrawal			
Lost to follow up			

9. Other Safety Parameters

Other safety parameters such as ECG, vital signs and physical examinations will be summarised

For laboratory parameters, observed values, changes from baseline, shifts in CTC grade and normal values/above and below normal values will be summarised with descriptive statistics. A listing of individual laboratory data will be provided with values outside normal ranges flagged.

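### Tumour-size change is summed over all lesions although some may be left untreated, and the tumour sampled for drug concentration is not required to be an embolised one

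*Protocol*

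**What the plan says.** Protocol 6.1.1, under the embolisation procedure, states that "it is not a requirement of the protocol that all lesions visible on CT are treated with BTG-002814" and leaves the choice to the treating investigator. Its example is a planned right hemihepatectomy, where "the lesions to be treated may be those deemed to be at highest risk of a positive surgical resection margin". The approach is superselective for HCC and generally lobar for mCRC. On records, "The vessels embolised will be noted and the amount of embolic agent used will be recorded", and bead position is checked by 4D CT, which Protocol 7.2.4 schedules at Visit 3.

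SAP 6.2 describes the size analysis: "The longest diameter of each lesion (mm) is measured at baseline and again on the day before surgical resection", and "The sum of the diameters can be taken for each patient, using the same lesions". The result goes into waterfall plots, for all patients and by disease. A test is optional: "Change in tumour size can also be compared using a paired t-test or Mann-Whitney test".

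SAP 4.2.2 describes tissue sampling as "malignant tissue – three measurements for each patient", at the centre, middle and edge of the tumour, with one non-malignant sample 1 cm outside it. The average of the three, minus the non-malignant value, gives a paired difference. Protocol 7.3.15 adds only that malignant and non-malignant resected liver will be assayed. Tissue concentration is part of a co-primary endpoint (Protocol 4.5.1); change in tumour size is not a Protocol endpoint at any level.

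**The concern.** The Protocol separates lesions into those the operator treats and those that may be left alone. Neither analysis carries that distinction forward. SAP Section 2 tabulates the number of liver lesions and the sum of longest diameters, so patients with several lesions are expected.

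For size, the wording of SAP 6.2 takes in untreated lesions. The reference to the same lesions fixes the set between the two scans; it does not limit the set to embolised tumour. In an affected patient the summed change then depends partly on how much of the disease the operator chose to treat. Because the plots are also shown by disease, and the catheter approach differs by disease, an apparent HCC versus mCRC difference could partly reflect the treated share.

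For tissue, the gap is silence about which tumour is sampled. If a patient with a treated and an untreated tumour yields a very low malignant concentration, nothing in the planned data shows whether the beads failed to deliver drug there or the tumour was never targeted. With a target of 6 patients per disease, one such value matters.

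**Working it through.** **The plan's own figures.** The plan gives no effect size, SD or lesion count for these analyses. Its sample size reproduces: 3 + 9 = 12, equal to 6 HCC + 6 mCRC; with two replacements, 12 + 2 = 14 (Protocol 9.1).

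**Size change.** Let f be the share of the baseline diameter sum lying in treated lesions, Dt the percentage change in treated lesions and Du the percentage change in untreated ones. All three are assumptions. Then

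change in the sum = f × Dt + (1 − f) × Du.

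With Dt = −20%, Du = 0 and f = 0.5: 0.5 × (−20) + 0.5 × 0 = −10%. Over a range:

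| Dt | Du | f = 1 | f = 0.75 | f = 0.5 | f = 0.25 |
|---|---|---|---|---|---|
| −10% | 0 | −10 | −7.5 | −5 | −2.5 |
| −20% | 0 | −20 | −15 | −10 | −5 |
| −20% | +5% | −20 | −13.75 | −7.5 | −1.25 |
| −30% | 0 | −30 | −22.5 | −15 | −7.5 |

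For equal-sized lesions with one treated, f is 1/2, 1/3 or 1/4 with two, three or four lesions, and −20% becomes −10%, −6.7% or −5%. If untreated lesions grow, the attenuation is worse. At f = 1 (a single treated lesion, or all lesions treated) it vanishes.

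**Tissue concentration.** Suppose k of n patients are sampled from an untreated tumour whose level is r times that of a treated one. Relative to sampling treated tumour throughout,

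group mean ratio = ((n − k) + k × r) / n.

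| n | r | k = 1 | k = 2 | k = 3 |
|---|---|---|---|---|
| 12 | 0 | 0.92 | 0.83 | 0.75 |
| 12 | 0.1 | 0.925 | 0.85 | 0.775 |
| 6 | 0 | 0.83 | 0.67 | 0.50 |
| 6 | 0.1 | 0.85 | 0.70 | 0.55 |

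At k = 0 the ratio is 1. The values of k and r are assumptions, and the documents do not say that k will exceed zero.

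**The case against.** The strongest reply is that the harm is conditional and the analyses are modest. Attenuation needs a patient with several lesions and at least one untreated, and no frequency is given. A lobar approach in mCRC may cover several lesions at once. Protocol 9.1 calls the analysis mainly descriptive and the study unpowered, the test in SAP 6.2 is optional, and the tissue results are plotted per patient, so an outlier would be seen. All of this stands and limits the weight of the point. It does not supply a rule for which lesions enter the sum, and a visible outlier still cannot be explained without knowing its source tumour.

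A reader might infer three stronger things that the documents do not support.

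- That effects and drug levels will be diluted. They can be, in some patients; how many is unknown.
- That the three tissue samples mix treated and untreated tumour. Centre, middle and edge read as positions within one tumour. The issue is only which tumour. The Protocol cites the Laboratory Manual for handling, storage and shipping, so it neither shows nor excludes a lesion-selection rule.
- That the optional test loses a definite amount of power. That requires an assumed SD and an assumption about how it changes as lesions are added. If untreated lesions are stable and all the variation comes from treated ones, mean and SD shrink together and power does not fall. In an unpowered study such figures carry no weight.

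Extending the criticism to necrosis (SAP 5.2) or perfusion (SAP 5.4) would need its own argument, which is not made here.

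**Conclusion.** The point holds in a limited form. For size change, SAP 6.2 as written includes untreated lesions wherever they exist, and the summed change is attenuated in proportion to the treated share of baseline diameter when those lesions are stable: an assumed −20% becomes −10% at a share of one half, and stays at −20% when everything is treated. For tissue concentration, the fault is an unrecorded source tumour. One affected patient among 6 with negligible drug would lower that group's mean by about 17% (1 − 0.83), but whether any patient will be affected cannot be known from the documents.

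The size part follows directly from the SAP wording. The tissue part rests on silence and is less certain, but touches a co-primary endpoint. Neither undermines the trial; both are worth correcting before analysis because the correction is small.

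**What to change.** **SAP 6.2.** Classify each lesion as targeted or not from the treatment plan and the recorded embolised vessels. Use the Visit 3 CT as confirmation only: a targeted lesion without visible beads stays in the targeted group, since defining the group by visible beads would select on successful delivery. Base the main sum of diameters, the waterfall plots and any test on targeted lesions. Show untreated lesions separately as a within-patient reference.

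**SAP 4.2.2.** Record the embolised status of the tumour each tissue sample came from. Present malignant concentrations, and the malignant minus non-malignant difference, for embolised tumours, and list any others separately. The source should be noted when tissue is collected, as it may not be recoverable later.

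**Cost.** SAP wording, a lesion-status field and a sample-source field with a matching line in the tissue-collection instructions. The Protocol records vessels, not lesion status, so someone must make the classification. The main size summary will contain slightly fewer lesions. The sample size and the choice of lesions to treat do not change.
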